## b. IDE-Exempt Devices

IND-Exempt Device 1	
Name:	NA
Description:	NA

---

## 6. DRUGS, BIOLOGICS, REAGENTS, OR CHEMICALS USED IN THE STUDY

---

### a. Investigational Drugs, Biologics, Reagents, or Chemicals

Investigational Product 1	
Name:	NA
Dosage:	NA
Administration Route:	NA

---

### b. Commercial Drugs, Biologics, Reagents, or Chemicals

Commercial Product 1	
Name:	Guanfacine hydrochloride immediate release
Dosage:	0.5mg nightly, increase every 3 days until 2mg nightly
Administration Route	Oral
New and different use? (Y/N)	Y

---

**7. DISINFECTION PROCEDURES FOR MEDICAL EQUIPMENT USED ON BOTH HUMANS AND ANIMALS**

NA

---

**8. PARTICIPANT POPULATION**

**a. Planned Enrollment**

25

**b. Age, Gender, and Ethnic Background**

18-69 years old, male and female, all ethnic backgrounds

**c. Vulnerable Populations**

Children younger than 18 are not included due to the fact that many of the clinical and biological measures that will be used in subsequent research studies in our clinic are validated for use in people 18 and older.

**d. Rationale for Exclusion of Certain Populations**

NA

**e. Stanford Populations**

If any Stanford employees, and/or students qualify and wish to participate, they will be treated the same as any other participant.

**f. Healthy Volunteers**

NA

**g. Recruitment Details**

[name] ongoing imaging trials will be leveraged. Recruitment pipelines include flyering, online advertisements, Facebook ads, and participants from an IRB-approved R01 grant, where approximately one participant per two weeks meets study criteria. Psychiatric symptoms are assessed during recruitment.

We will also use online advertisements through the lab's Facebook platform, where all comments are private to prevent inadvertent PHI sharing. Advertisements will be IRB-approved before launch.

Participants will provide written informed consent, adhering to Stanford IRB guidelines and the Declaration of Helsinki

---

**h. Eligibility Criteria**

**i. Inclusion Criteria**

- 18-69 years of age (inclusive)

- Go-NoGo fMRI task-evoked dLPFC  $\leq$  - 0.5 SD below the mean of normative sample
- Behavioral cognitive control performance  $\leq$  - 0.5 SD below the mean of normative sample on a Maze, Digit Span, and/or Verbal Interference (Stroop) task administered using WebNeuro
- Score  $\geq$  14 on the 17-item Hamilton Depression Rating Scale-17 (HDRS-17)
- Meets DSM-5 diagnostic criteria for current, past, or recurrent nonpsychotic major depressive disorder established by MINI Plus
- Medication naïve to guanfacine
- Fluent and literate in English, and show non-impaired intellectual abilities to ensure adequate comprehension of the task instructions
- Written, informed consent
- fMRI scanning eligibility, including no evidence of any form of metal embedded in the body (e.g., metal wires, nuts, bolts, screws, plates, sutures), as these produce artifacts when brain imaging. All potential subjects will need to successfully complete the screening forms at the Stanford Center for Cognitive and Neurobiological Imaging (CNI).

ii. Exclusion Criteria

- Presence of suicidal ideations representing imminent risk, defined by a score of  $>$  8 on the MINI-Plus, or by clinician judgement
- Lifetime history of medical illness or injury that may compromise cognitive functioning or interfere with assessments as deemed by the study physician (such as neurological disorders such as seizures or stroke, Parkinson's disease, dementia, or traumatic brain injury)
- Severe impediment to vision, hearing, and/or hand movement likely to interfere with ability to complete the assessments, or are unable and/or unlikely to follow the study protocols
- Pregnant, breastfeeding or unwilling or unable to use adequate birth control throughout the study
- Loss of consciousness for  $>$  10 minutes during lifetime
- Any contraindication to being scanned in the 3.0T scanner at the CNI such as having a pacemaker or implanted device that has not been cleared for scanning at 3.0 Tesla
- Previous or current DSM-5 bipolar disorder (I, II, not otherwise specified) or psychosis
- Meets criteria for DSM-5 alcohol or substance use disorder within the last 12 months
- Meets criteria for current DSM-5 PTSD, OCD, or eating disorder
- Concurrent participation in other intervention or treatment studies
- Current use of psychotropic medications. If their usual treating physician is supportive, participants who are currently on psychotropics that can be safely tapered may be tapered off to participate but participant must wait 5 half-lives prior to first scan
- Current use of a strong CYP3A4 inhibitor or inducer (macrolide/ketolide antibiotics [clarithromycin, telithromycin], azole antifungals [itraconazole,

ketoconazole, posaconazole, voriconazole], protease inhibitors [atazanavir, darunavir, indinavir, lopinavir, nelfinavir, ombitasvir, paritaprevir, ritonavir, saquinavir], ceritinib, cobicistat, and idealisib), or inducer (apalutamide, carbamazepine, enzalutamide, fosphenytoin, lumacaftor, lumacaftor-ivacaftor, mitotane, phenobarbital, phenytoin, primidone, rifampin)

- Hypotension as defined by SBP  $\leq$  90 and/or DBP  $\leq$  60 on 2 of 3 separate measurements at least 5 minutes apart, bradycardia as defined by HR  $\leq$  55 on 2 of 3 separate measurements at least 5 minutes apart
- General medical condition, disease, or neurological disorder as reported by participant or found on in-person screenings that is deemed by the study physicians to be unsafe for GIR treatment, including kidney or liver impairment that is deemed to be unsafe, EKG abnormalities that are deemed to be unsafe, or cardiovascular disease deemed to be unsafe.
- History of sudden cardiac death in first degree relatives
- Positive drug screen for any substance deemed by the study physician to be unsafe for use with GIR in combination with other information obtained during screening

---

i. **Screening Procedures**

Participants will complete an online eligibility survey, provide informed consent, and attend two screening visits. Screenings include clinical interviews, medical history, cognitive testing, and functional MRI scans to assess dLPFC activation.

---

j. **Participation in Multiple Protocols**

Participants will first be screened via an online REDCap survey in order to determine initial eligibility. Once participants have completed the survey and have been determined eligible, they will continue to an in-person visit where consenting will take place and further screening procedures will be completed.

Participants will be screened for assessment of inclusion and exclusion criteria at the in-person baseline visit. We will ensure that consent is obtained and enrollment completed before personal health information is collected.

We also screen using the following physical and laboratory tests:

a) **Physical Exam:**

- Participants will be asked to provide additional details of their medical history specifically relevant to the treatment contraindications (exclusion criteria). For standard monitoring, we will assess height, weight, vital signs, systems assessment, and general medical presentation during the physical exam.

b) **Laboratory Testing:**

- For standard monitoring, we undertake the following:
  - **Blood sample:** Analyzed for CBC, CMP, LFTs, TSH, and serum pregnancy test.
  - **Urine sample:** For urine drug screen.
  - **Electrocardiogram (EKG):** To assess cardiovascular health.

---

k. **Payments to Participants**

Research subjects will be offered [REDACTED] for the pretreatment fMRI session, self-report questionnaires, and cognitive assessments; and [REDACTED] for the subsequent MRI session at Week 8 of the treatment phase. Participants who complete the Monetary Incentive Delay (MID) task in the three MRI sessions will be offered an additional payment depending on their performance on the task, for a maximum total of [REDACTED] per session.

Participants will be compensated [REDACTED] for each of the 5 phone visits with completed questionnaires, [REDACTED] for the virtual or in-person physician check-ins at Weeks 2 and 8, and [REDACTED] for the physician check-ins at Weeks 4, 6, and 10.

---

## **I. Costs to Participants**

No protocol-related costs will be charged to participants.

---

## **m. Planned Duration of the Study**

The probable duration of the entire study is three years.

### **1. Individual Participant Duration:**

- Screening: Approximately four hours.
- Active Participation: Approximately 24 hours total over 12 weeks, with 10–12 days of active engagement.
- Total Study Duration: Participants will spend about 12 weeks enrolled in the study, including an 8-week treatment phase and follow-up activities.

### **2. Study Completion Timeline:**

- The study is planned to be conducted over three years, with data analysis for each participant requiring approximately 160 hours.

---

## **9. RISKS**

---

### **a. Potential Risks**

#### **i. Investigational devices**

NA

#### **ii. Investigational drugs**

NA

#### **iii. Commercially available drugs, biologics, reagents or chemicals**

Guanfacine Side Effects and Potential Risks in Children and Adolescents with ADHD: Drowsiness (28% to 57%), headache (16% to 28%), fatigue (10% to 22%), dizziness (4% to 16%), insomnia (2% to 13%), abdominal pain (8% to 19%), decreased appetite (5% to 15%), hypotension (4% to 9%), bradycardia (2% to 5%), orthostatic hypotension (1% to 5%), first-degree atrioventricular block (≥2%), sinus arrhythmia (≥2%), tachycardia (≥2%), syncope (1% to ≥2%), irritability (5% to 8%), lethargy (3% to 8%), anxiety (2% to 5%), nightmares (3% to 4%), emotional lability (2% to 3%), agitation (≥2%), depression (≥2%), increased blood pressure (≥2%), loss of consciousness (children: ≥2%), skin rash (2% to 3%), pruritus, weight gain (2% to

3%), xerostomia (3% to 8%), nausea (5% to 7%), vomiting (2% to 7%), diarrhea (2% to 6%), constipation (2% to 4%), abdominal distress ( $\geq 2\%$ ), dyspepsia ( $\geq 2\%$ ), stomach discomfort ( $\geq 2\%$ ), urinary incontinence (2% to 5%), asthma ( $\geq 2\%$ ), fever (8%; Biederman 2008).

iv. Procedures

**Risks Associated with fMRI**

Magnetic fields do not cause harmful effects at the levels used in the MRI machine. However, the MR scanner uses a very strong magnet that will attract some metals and affect some electronic devices. Participants will be screened for having cardiac pacemakers or any other biomedical device in or on their body, including any metal objects (especially surgical clips), devices, or implants before entering the magnet room. All such objects will be removed (if possible) before entering the magnet room. In some cases, having those devices means participants should not have an MRI scan performed. Participants will also be screened for history of head or eye injury involving metal fragments, having worked in a metal shop, or for being pregnant. They will also be asked for any tattoos on their body, including eyeliner and other permanent makeup. Tattoos could become warm and irritated during the scan and remain so for several days. There is a possibility that participants will experience a localized twitching sensation due to the magnetic field changes during the scan. This is expected and should not be painful. There is a small risk of heating from the cables associated with these devices. Dizziness or nausea may occur if participants move their head rapidly within the magnet. The scans performed in this study are for specific research purposes and are not optimized to find medical abnormalities. The investigators for this project may not be trained to perform medical diagnosis. However, on occasion the investigator may notice a finding on an MRI scan that seems abnormal.

**Distress During Interviews**

The interviews are time consuming and about personal matters. It is possible that participants will feel upset, tired, or anxious.

**Phlebotomy**

There is a minimal risk of infection with blood draw as well as the risk of minor discomfort.

v. Radioisotopes/radiation-producing machines

NA

vi. Physical well-being

NA

vii. Psychological well-being

Some participants may experience distress or anxiety related to participating in the procedures. Participants will be monitored throughout the procedures and encouraged to report any concerns. A psychiatrist will be available to assist the participant if

needed, and participants will be removed from the protocol if their distress or anxiety becomes intolerable.

- viii. Economic well-being  
NA
- ix. Social well-being  
NA
- x. Overall evaluation of risk

Low - innocuous procedures such as phlebotomy, urine or stool collection, no therapeutic agent, or safe therapeutic agent such as the use of an FDA approved drug or device.

---

**b. International Research Risk Procedures**

NA

---

**c. Procedures to Minimize Risk**

**Participants are safeguarded from undue risk by procedures to obtain informed consent, ensure confidentiality, and minimize possible risks associated with the study.** Each is described below.

Potential risks associated with participation in this study may include the potential for the following:

1. Distress from completing cognitive and psychological questionnaires and from being in an fMRI scanner.
2. Risks associated with blood, saliva, and urine sampling.
3. Risks associated with GIR administration.

The risks are reasonable in relation to the anticipated benefits and will be minimized by using procedures that are consistent with sound research design, that do not unnecessarily expose participants to risk, and that are based on established research and trial protocols.

**Questionnaires:**

The risks associated with the self-report and clinical assessments are minimal. Research personnel are trained to manage any distress that is generated by completing these assessments, and protocols for managing any distress have been well established in prior studies. Some participants might experience discomfort with discussing personal information with a person they do not know.

**Behavioral and Cognitive Assays:**

The risks associated with the behavioral and cognitive assessments are also minimal. Research personnel are trained to manage any distress that is generated by completing these assessments, and protocols for managing any distress have been well established in prior studies.

**Brain Imaging Assays:**

The principal piece of equipment used in this protocol is a 3 Tesla GE fMRI scanner. A small number of people may feel claustrophobic inside the machines. The study will be

immediately stopped via button press if this occurs. Study personnel and technicians will be on-site during all acquisitions to address any such discomfort. To minimize fatigue, sufficient breaks are provided to participants during the scanning procedure, and the experimenter regularly inquires as to whether there is anything that they can do to facilitate the participant's comfort. The risks associated with fMRI are minimal. Routine contraindications to MRI include the presence of any metal implants (pacemaker, aneurysm clips, neurostimulators, cochlear, eyes, tattoos with ink contraindicated for fMRI scanning). The scan will be immediately stopped via button press if this occurs. Study personnel and MRI technologists will be on-site during all acquisitions to address any such discomfort.

**Blood and Urine Sampling:**

Blood and urine samples will be required prior to entry to assess for health problems, drug use, and pregnancy (in females). Participants may experience minor discomfort.

**Saliva and Hair Sampling:**

Saliva and hair samples will be collected as optional components of the study. Participants may experience minor discomfort.

**Guanfacine:**

GIR studies have reported blood pressure changes in patients with ADHD as well as in healthy control participants. Any medical risks from decreased blood pressure will be minimized through the careful screening of potential participants. Potential participants with baseline hypotension, history of cardiovascular illness, or concerning findings on EKG will be excluded. If a participant experiences distressing side effects, GIR will be discontinued. Participants will be closely monitored through in-person and bi-weekly phone assessments to assess safety and tolerability, specifically asking about known side effects detailed above. Bloodwork and physician examination with their PCP will be arranged as needed. Participants will be reminded that they can elect to terminate study participation at any time, and if experiencing significant distressing side effects, drug administration will be discontinued.

**Other Considerations:**

**• Incidental Findings on MRI:**

Although this study and scans from this study will be used for research purposes, we will also collect T1-weighted anatomical images from each participant. We will follow the IRB-approved protocol of CNI or the Lucas Center, whereby any indications of an incidental finding are sent to a neuroradiologist for a clinical report.

**• Emergencies:**

If, during the course of interviewing and assessment procedures, study staff identifies a condition that mandates immediate clinical intervention or official reporting, all necessary steps will be taken, and the emergency procedures of the institution will be followed. In the event that a research participant expresses suicidal ideation during a clinical interview or when completing a questionnaire, a suicide risk assessment will be performed, and a licensed clinical psychologist or psychiatrist will be consulted in order to determine the level and immediacy of risk. If the research subject is deemed an imminent danger to self, they will be placed on a 5150 LPS psychiatric hold and transferred to Stanford Hospital Emergency Department for comprehensive clinical evaluation and assessment.

---

**d. Study Conclusion**

**Emergencies:**

If, during the course of interviewing and assessment procedures, study staff identifies a condition that mandates immediate clinical intervention or official reporting (e.g., homicidality or suicidality), all necessary steps will be taken, and the emergency procedures of the Department of Psychiatry and Behavioral Sciences will be followed. In the case that staff determine that the participant is at significant risk for self- or other-destructive behavior, necessary treatment steps will be taken (e.g., hospitalization, referral to a care provider, etc.). All participants will be given numbers to call in the event of an emergency during treatment: the primary phone number of the treating clinician and the number for the clinic. If the treating clinician is immediately unavailable, participants will be instructed to not delay and to go to their nearest Emergency Room.

**Safety Measures Upon Termination:**

After a participant's completion of or early termination from the study, participants will be followed up only in the case of an adverse event. If an adverse event occurs, the participants will be followed by the study MD until the adverse event is resolved. Referrals will be given if needed.

**Termination Due to Loss to Follow-Up:**

Staff will call participants who miss a visit on the same day to inquire about reasons for the absence, help problem-solve, and reschedule the missed visit. Staff will be persistent in attempting to re-engage noncompliant participants in subsequent follow-ups via phone and/or email. Participants are considered lost to follow-up if they miss a scheduled visit and are unresponsive to three subsequent attempts to reach them. Staff will encourage participants lost to follow-up to contact their standing psychiatrist for ongoing care. Additionally, we will email any participants lost to follow-up our mental health resource guide to provide them with local and national mental health care resources.

---

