**a. Procedures**

1. Recruitment and screening: Participants experiencing depressive symptoms and not taking any psychiatric medications as determined by a 5 half-life wash out period will be recruited from the community, including students and employees at Stanford. Recruitment will come primarily from Facebook ads, which will use only IRB approved material. A flyer will also be physically posted on boards in public locations in order to include a variety of sources for the study.
2. Individuals will need to participate in 3 screening visits in order to enroll in the study. During the first visit, participants will review informed consent, be administered a clinical interview, and be sent instructions for completing cognitive testing at home.
3. If eligibility after this initial screening visit, the second visit will be a medical screen in order to ensure participants are safe to take GIR and will include standard blood tests, medical history, vitals, and a urine drug test.
4. If the participant meets medical and cognitive criteria, functional magnetic resonance imaging (fMRI) scans will be undertaken at another study visit at The Stanford Center for Cognitive and Neurobiological Imaging (CNI). Using a participant's task-evoked activity

in the dorsolateral prefrontal cortex (dLPFC) and performance on objective cognitive testing, we will apply thresholds using established healthy norms to select participants within the cognitive biotype+ group.

5. Participants will receive GIR for a period of 8 weeks sent to their place of residence from Mariner pharmacy.
6. Participants will be seen in-person or virtually by a study clinician at weeks 2, 4, 6, 8, and 10 and an appropriately trained clinical research coordinator at weeks 1, 3, 5, 7, and 9. All subjects will have an fMRI scan after 6-8 weeks of taking GIR. During in-person visits and virtual monitoring, we will assess participants for the following: changes to symptoms, function, and suicidality, adherence to GIR, changes to concomitant medication(s), adverse events (AEs), birth control usage compliance, likelihood of pregnancy (female participants of childbearing potential), and vital signs if appropriate.

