**g. Study Endpoint(s)**

The endpoint for primary and secondary measures will be 8 weeks after initiation of GIR or placebo, regardless of the study outcomes. Additional measures will be collected at the final endpoint of 10 weeks. If a subject reports a significant adverse event or worsening depression, the participant will be removed from the study. The study will not be terminated prematurely in the event that participants randomized to GIR have greater improvement than participants randomized to placebo.

---

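### The loss-to-follow-up rule can close a participant from week 1, and nothing in the plan provides for collecting the week-8 data afterwards

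*Protocol*

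**What the plan says.** The rule is in Protocol section 9.d, under the heading "Termination Due to Loss to Follow-Up". Its trigger is: "Participants are considered lost to follow-up if they miss a scheduled visit and are unresponsive to three subsequent attempts to reach them".

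The same paragraph also requires outreach. "Staff will call participants who miss a visit on the same day to inquire about reasons for the absence", and they are to help solve the problem and rebook. It adds: "Staff will be persistent in attempting to re-engage noncompliant participants in subsequent follow-ups via phone and/or email". For those classed as lost, it lists two actions: encouragement to contact their own psychiatrist, and an emailed resource guide.

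The paragraph just before it, on safety measures upon termination, covers completers and early terminators alike: "participants will be followed up only in the case of an adverse event".

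Protocol section 2.a sets the contacts. Participants are "seen in-person or virtually by a study clinician at weeks 2, 4, 6, 8, and 10", and meet an "appropriately trained clinical research coordinator at weeks 1, 3, 5, 7, and 9". Section 8.k (payments) counts five of the contacts as phone visits.

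Section 2.g fixes the time of analysis: "The endpoint for primary and secondary measures will be 8 weeks after initiation of GIR or placebo". Section 2.a places the post-treatment scan after 6 to 8 weeks of drug. The SAP compares pre- with post-treatment sessions and handles missing data by listwise deletion.

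**The concern.** The trigger is tied to any one scheduled visit, while the outcome that counts comes at week 8. Three calls within a few days would satisfy it. A participant who goes quiet early could therefore be closed weeks before the endpoint, although being out of touch in week 1 or 2 does not show that the person could not attend a scan in week 8.

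Once the person is closed, two other provisions make the status matter. Follow-up after early termination is for adverse events only, and a participant without a post-treatment scan leaves the primary model. With a planned enrolment of 25, each such person is 1/25 = 4% of the sample. Staff reading section 9.d also cannot tell whether re-engagement should go on after the third failed attempt, so similar cases may be handled differently.

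**Working it through.** **1. What the provisions imply together**

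| Question | What the text gives | Where |
|---|---|---|
| What triggers the status? | One missed scheduled visit and three unanswered attempts | Protocol 9.d |
| Minimum time, spacing, consecutive misses or study week? | None stated | Protocol 9.d |
| Does outreach continue after the status is set? | Not stated | Protocol 9.d |
| What follows early termination? | Follow-up for adverse events only | Protocol 9.d |
| Is a week-8 scan or test offered after termination? | No provision found | Protocol, SAP |
| What happens to a case with no post-treatment data? | Deleted listwise | SAP, missing data |

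If re-engagement is meant to continue after the status is set, it conflicts with the adverse-event-only sentence and the termination heading. If it is meant to stop, nothing in the plan leads back to the week-8 assessment.

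**2. How early the rule can apply**

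The clinician and coordinator schedules together give one contact per week, so seven contacts (weeks 1 to 7) precede week 8. A week-1 trigger falls 8 − 1 = 7 weeks before the endpoint. If phone contacts were not counted as scheduled visits, the first possible trigger would be the week-2 clinician visit, 8 − 2 = 6 weeks before it.

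**3. How often it might apply (illustration)**

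The plan gives no dropout rate, so there is no figure of its own to reproduce. Let q be an assumed chance, per contact, of a miss followed by three failed attempts. The chance of being classed as lost before week 8 is 1 − (1 − q)^7.

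| Assumed q | Classed as lost | Expected number of 25 |
|---|---|---|
| 0.5% | 3.4% | 0.9 |
| 1% | 6.8% | 1.7 |
| 2% | 13.2% | 3.3 |
| 3% | 19.2% | 4.8 |
| 5% | 30.2% | 7.5 |

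Seven contacts is the upper count, because a scan at week 6 would have fewer before it.

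**4. What losses of that order would cost (illustration)**

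Inputs: N = 25 (Protocol 8.a); two-sided 0.05 (SAP); assumed standardised mean change dz = 0.5; assumed losses of 3 or 5, close to the rows for q = 2% and 3%. The calculation is for one paired t-test, which the SAP plans for the individual circuit measures. It does not describe the multi-measure general linear model.

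- The 95% half-width, in SDs of change, is t(0.975, n − 1)/√n.
- Power comes from the noncentral t distribution with noncentrality dz × √n.

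| Completers | Half-width | Relative to 25 | Noncentrality | Power | dz detectable at 80% |
|---|---|---|---|---|---|
| 25 | 2.064/5.000 = 0.4128 | – | 2.500 | 0.67 | 0.58 |
| 22 | 2.080/4.690 = 0.4434 | +7.4% | 2.345 | 0.61 | 0.63 |
| 20 | 2.093/4.472 = 0.4680 | +13.4% | 2.236 | 0.56 | 0.66 |

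These are upper bounds on what the wording costs. They suppose that a changed rule would recover everyone, yet some of these people would be unreachable under any rule.

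**The case against.** The strongest reply is that the rule applies only to people who miss a visit and also fail to answer three times, and that the same paragraph already requires a same-day call, rescheduling and continued re-engagement. Anyone who answers stays in. The reference to subsequent follow-ups can fairly be read as later scheduled contacts, which is close to what is asked for here. No sentence refuses a participant who reappears.

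Much of this stands, and it rules out several stronger readings that a reader might infer:

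- *That available participants are written off.* The documents do not say so. They leave open whether such a person is still invited at week 8.
- *That every outcome is read only once, so nothing else exists on these people.* Symptoms and function are assessed at interim contacts, and further measures are taken at week 10. The narrower fact is that week 8 is the analysed endpoint.
- *That the rule removes sicker, sedated or non-adherent people selectively and so biases the result.* This is plausible, but neither document gives evidence on who misses contacts.
- *That the rule ends the weekly mood and suicidality checks.* Non-response itself prevents those checks while it lasts.

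What the reply does not settle is the position after the third failed attempt. The same-day call and rescheduling help those who respond, whereas the definition concerns those who do not. The re-engagement sentence comes before the definition and has no stated duration. If it is read as continuing, it contradicts the adverse-event-only sentence in the paragraph before.

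**Conclusion.** The concern holds as a gap in the rules for data collection. As written, a participant can be classed as lost from week 1, with no minimum interval, under a heading that treats this as termination. Follow-up after termination is confined to adverse events, and listwise deletion then removes anyone without the post-treatment data. A person who might still have given the week-8 scan and tests may therefore be missing from the primary analysis.

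The size cannot be fixed from the documents. The power and interval figures rest on an assumed dz of 0.5 and assumed losses of 3 or 5, and the part due to wording alone could be much smaller. This is a moderate point that is worth acting on because the remedy is inexpensive; it does not decide whether the trial can answer its question.

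**What to change.** In Protocol section 9.d:

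1. Record a missed contact as a missed contact only.
2. State that outreach continues at each later scheduled contact.
3. Offer the week-8 scan, cognitive tests and scales whether or not earlier contacts were missed, unless consent is withdrawn.
4. Assign lost-to-follow-up status, for data purposes, only when the week-8 to week-10 window has closed without contact.
5. Amend the paragraph on safety measures upon termination so that early termination does not exclude outcome collection.

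The SAP's missing-data paragraph should then report how many participants lack week-8 data and for what reason.

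The change covers data collection only. Keeping a record open for an uncontactable participant touches on drug supply and on the safety follow-up and end-of-treatment text (Protocol sections 2.a and 9.d). The sponsor must reconcile those passages, and no clinical rule is proposed here.

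The cost is protocol wording, a few more calls by existing staff, and records that stay open some weeks longer.
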